### **Background, Rationale and Context**

Pain can have a significant impact on psychiatric patients, as it can exacerbate symptoms and interfere with treatment. Pain can cause or worsen anxiety and depression, is associated with increased disability and poorer quality of life in people with severe and persistent mental illness. (Birgenheir et. al., 2013, Onwumere et al., 2022, Stubbs et al., 2015). Additionally, both severe and persistent mental illness and pain are associated with increased suicide risk (Fu XL et al., 2021, Racine, 2015).

Evidence suggests that individuals with mental illness may be one population with particularly high rates of chronic non cancer pain (CNCP) and may also be more likely to receive prescription opioids for their pain (6). Individuals with serious mental illness, who are most at risk for developing opioid-related problems, continue to be prescribed opioids more often than their peers without mental illness (Owen-Smith et al., 2020).

As of January 1, 2018, The Joint Commission requires hospitals to have non-pharmacologic modalities available for pain management in an effort to decrease the need for opioids. Acupuncture and acupressure have been used for centuries in the management of a variety of disorders including pain. A recent meta-analysis (Zhong et al., 2019) of 26 RCTs (all included studies were in China) favored the use of acupressure for pain management over usual care based on total effective rate (RR =1.25, [CI= 1.13, 1.37], p <.0001) and total analgesia use (RR=0.41, [CI= 0.24, 0.68] p = .0006). There were no serious adverse events reported in the 26 trials (N=1063 in treatment groups) and no withdrawals from the studies were reported due to adverse events. More recently, in an effort to increase access to non-pharmacological modalities for pain management, the VA has developed a **battlefield auricular acupressure (BAApress) protocol**. Unlike acupuncture, acupressure can be easily applied with training and is within the scope of practice for nurses, according to the North Carolina Board of Nursing (NCBON, 2013). Although acupressure has been used for centuries in traditional Chinese medicine, there are few studies assessing the use of nurse-initiated acupressure as an adjuvant for co-occurring pain. Thus, we propose assessing the effectiveness of BAApress for chronic and acute pain management for psychiatric patients in a psychiatric emergency room setting. In addition, by analyzing measures and demographics we hope identify patients that may benefit most from BAApress acupressure.

This feasibility study is being performed in collaboration with the BAApress training and Intervention Fidelity study IRB00084011. This study is similar to Fidelity study IRB00068022, Auricular Acupressure for Pain Management as a Non-Opioid Adjuvant Therapy for Opioid Tolerant Patients (PI [name]). The purpose of this study is to test the feasibility of Emergency Department nurse-initiated battlefield auricular acupressure as an adjunct to medication for pain management for psychiatric Emergency Department Observation patients.

The Battlefield Auricula Acupressure interventionists (nurse) will complete Auricular training modules and complete competency assessments and intervention assessments throughout the study. Study interventionist will include the possibility that a study participant may be part of a competency assessment and that their session may be recorded and securely uploaded to a server per IRB and institutional policies.

### **Objectives**

1. To determine psychiatric patients' acceptance of BAApress as an adjunct treatment to address co-occurring pain.
2. To determine if the addition of BAApress protocol will lower pain scores and decrease pain medication usage.
3. To determine ability of ED nurses to incorporate BAApress into their workflow.

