### **Methods and Measures**

#### **Design**

Feasibility trial, no control group

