**Day 1**

The baseline and day 1 activity can take place on the same day, but it is not required. Following completion of informed consent and baseline questionnaires, the trained BAApress interventionist nurse will place the acupressure pads.

- If the ear contains lesions, skin breakdown, or show signs of irritation, the acupressure pads will not be placed, and this will be noted in the study record.
- If the participant consented to the recording portion of the study, they will be reminded of the process and the BAApress acupressure nurse will confirm that the participant still agrees to participate in the recording portion of the study.
- Acupressure pads will be placed prior to any pain medication.
- A total of 10 adhesive acupressure pads will be placed, 5 acupressure pads per ear. Patients will be given a handout showing location of each point where acupressure pad will be placed. The pads will be placed bilaterally on the following 5 auricular sites: 1) Cyngulate gyrus, 2) Thalamus, 3) Omega 2 4) Point Zero, and 5) Shen Men. These sites were selected based on the Veterans Administration Battlefield Auricular Acupressure Protocol for acute and chronic pain. This is the protocol the Veterans Administration uses for acupressure therapy for acute and chronic pain management and is taught to both nurses and physicians.
- Each ear will be cleansed with alcohol, beginning at the base of the ear (lobule) to the apex. The acupoints will be visually located and marked with a sterile surgical marker.
- The pads will be placed by visual identification of the preselected acupoints as per BAApress protocol. The pads will be placed on the identified site by hand or with the assistance of tweezers, with the seed portion of the pad aligning with the identified acupoint.
- To secure the pad, gentle but firm pressure will be applied to the pad, making sure that pressure is applied to the entire pad.
- After placement, the interventionist will apply moderate pressure to each acupressure pad for 30 seconds (total time 2.5 minutes per ear). Both right and left ear site will be stimulated at the same time with pressure in the following order: 1) Cyngulate gyrus, 2) Thalamus, 3) Omega 2, 4) Point Zero, and 5) Shen Men.
- Participants will tell the BAApress interventionist nurse when they feel a tingling sensation in the ear or feel moderate tenderness or pressure as confirmation

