### **Primary Outcomes**

Patient reported pain and general activity scores (Visual Analogue Scale) and (Brief Pain Inventory)

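### Objective 2 asks whether adding BAApress lowers pain and analgesic use, but a single-arm study given alongside medication can describe change and cannot attribute it to BAApress

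*Combined protocol and SAP*

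**What the plan says.** Objectives, item 2: "To determine if the addition of BAApress protocol will lower pain scores and decrease pain medication usage". Items 1 and 3 concern patient acceptance and nurse workflow.

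Background, Rationale and Context contains two statements of aim. One reads "we propose assessing the effectiveness of BAApress for chronic and acute pain management". The other reads "The purpose of this study is to test the feasibility of Emergency Department nurse-initiated battlefield auricular acupressure", and describes the intervention "as an adjunct to medication for pain management".

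The Design entry is "Feasibility trial, no control group", and the Analytical Plan repeats that there is no control group. Primary Outcomes names the VAS and the Brief Pain Inventory (BPI). Pain medication usage, acceptability and the nurse placement survey are secondary.

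On timing, the Day 1 section says "The baseline and day 1 activity can take place on the same day, but it is not required" and also "Acupressure pads will be placed prior to any pain medication". Footnote a of the schedule requires baseline activities to precede acupressure. The schedule lists a VAS and a BPI at baseline and again on Day 1.

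The Analytical Plan targets 10 to 20 participants. It begins with descriptive statistics, allows chi-square tests, t-tests or ANOVA for any group comparisons, and says the data will supply estimates for powering later studies.

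**The concern.** Asking whether the addition of a treatment will lower a score is a question about the effect of that treatment. Answering it needs some account of what would have happened without the treatment, and the plan provides none. The causal question is also attached to the primary outcome, while the outcomes that fit the feasibility purpose are secondary.

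As Objective 2 stands, a fall in pain over the study days invites the answer that BAApress lowers pain, and lower analgesic use invites the matching answer for medication. Neither conclusion would be supported. The same uncontrolled change could then be taken as the expected treatment effect when a later trial is powered, because the Analytical Plan does not say which estimates will be carried forward.

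**Working it through.** The plan contains no computed figure to reproduce. The target of 10 to 20 comes without alpha, power, effect size or SD. The check is therefore one of logic, followed by the precision the planned size allows.

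**1. What a change from baseline estimates.** For each participant let D be the end-of-study score minus the baseline score. Its mean can be written

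E(D) = δ + β + γ

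- δ is the effect of BAApress.
- β is change after placement from everything else: medication, other care, natural course, regression to the mean and expectation.
- γ is change between the baseline assessment and pad placement.

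Objective 2 asks about δ. A single arm estimates only the sum.

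**2. Whether the documents let β or γ be set to zero.**

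- *Medication.* BAApress is given in addition to it. Pads go on before pain medication, so later scores may follow both. β cannot be assumed zero.
- *Natural course, regression to the mean and expectation.* Participants enter with documented pain at an emergency psychiatric admission and know they are receiving the intervention. The eligibility criteria set no minimum pain score, so regression to the mean is not forced by a cut-off, but it is not excluded.
- *Gap before placement.* Baseline must precede placement but need not be on the same day. When it is earlier, γ enters D. The Day 1 VAS in the schedule is not timed relative to placement, so it does not close the gap as written.

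**3. Precision from the planned size.** The 95% confidence interval half-width for the mean within-participant change, in units of the SD of change, is t(0.975, n−1)/√n.

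- n = 10: 2.262/3.162 = 0.715, or 0.72 SD.
- n = 20: 2.093/4.472 = 0.468, or 0.47 SD.

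These are best cases, since they assume that every participant supplies paired data. The protocol foresees discharge before 3 days with telephone or text follow-up. If, as an assumption, 8 of 10 or 16 of 20 gave pairs, the half-widths would be 2.365/√8 = 0.84 SD and 2.131/√16 = 0.53 SD.

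**4. Whether size is the remedy.** The half-width shrinks with n, but β and γ do not. A larger single arm gives a tighter estimate of δ + β + γ and still says nothing about δ alone.

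**5. The endpoint of the change.** End of Study Assessment refers to day 5 questionnaires, while the schedule column is Day 3/End of study. Until these are reconciled, the change from baseline to end of study is not uniquely defined.

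**The case against.** The strongest reply is that the study is openly an uncontrolled feasibility study. Its purpose is stated as feasibility, the missing control group is declared twice, and the analysis starts with descriptive statistics. On that view Objective 2 is loosely worded and nothing more. Most of this stands, and it limits how serious the point is. It does not remove the point: declaring a design does not make it answer an objective it cannot answer, and that objective concerns the primary outcome.

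Several stronger readings are tempting, and the documents do not support them.

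- *The plan will test efficacy with an invalid before-after test.* No within-participant test, efficacy threshold or significance level is specified. The t-tests and ANOVA are for group comparisons that are left undefined.
- *The chance of a misleading positive result can be quantified.* That needs an assumed background fall, for which the documents give no figure, and a decision rule that the plan does not contain. No such probability is given here as the size of the problem.
- *The effectiveness sentence also covers medication use.* It speaks only of pain management. Medication use comes from Objective 2 alone.
- *There is no baseline for medication use.* The protocol body gives no reference period, and the history it describes is duration in years. But the Data Collection Form (Appendix A) is scheduled at baseline and Days 1 to 3, and its content is not in the text available. It may record prior use, so this is missing detail in the body and not a demonstrated absence.
- *The sponsor intends to power a later trial on the mean change.* The Analytical Plan does not say so. It leaves the choice open.

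**Conclusion.** Objective 2 and the effectiveness sentence are wrong as written: they pose a causal question that a single-arm study with BAApress added to medication cannot answer. This is a mismatch between objective and design and should be fixed. It does not prevent the study from meeting its feasibility purpose, and it does not call for a control arm or more participants.

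What the study can deliver is an estimate of within-participant change during BAApress plus usual medication. Its 95% half-width is at best 0.72 SD of change at n=10 and 0.47 SD at n=20. Those figures assume complete pairs and a t-based interval. The documents give no SD, so they cannot be turned into VAS or BPI points. The conclusion about attribution depends on none of these numbers; it follows from the absence of a comparator and the concurrent medication.

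**What to change.** (a) Reword Objective 2 along these lines: *to estimate, with 95% CI, the within-participant change in VAS and BPI from pre-placement baseline to end of study, and to describe analgesic use by day, during BAApress plus usual medication.* Bring the effectiveness sentence in the Background into line, and state that no effect of BAApress will be concluded. Reconcile the end-of-study time, which is day 5 in End of Study Assessment and Day 3 in the schedule, so that the change has one definition.

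(b) Use a VAS taken immediately before pad placement as the analysis baseline. The VAS already scheduled on Day 1 can serve if it is timed before placement. This removes the gap between baseline and placement for the VAS. It does not remove confounding by medication, and if the BPI stays at an earlier baseline the gap remains for that measure.

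(c) In the Analytical Plan, name what is carried into future power calculations: the SD of the outcome with its confidence interval, the within-patient correlation and attrition. State that the uncontrolled mean change will not be used as a treatment effect.

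The cost is a less ambitious stated aim, edits to the text, and at most one extra VAS for a participant whose baseline is on an earlier day. No additional participants are needed.

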### **Methods and Measures**

#### **Design**

Feasibility trial, no control group

#### **Setting:**

This study will utilize the location of Atrium Health Behavioral Health Charlotte Emergency Department ED and Observation unit for initiation of study procedures.

### **Subject Selection Criteria**

Any patient admitted to Behavioral Health Charlotte Emergency Department Observation Unit for psychiatric reasons and with co-occurring pain.

- **Inclusion Criteria**

Patients requiring admission to psychiatric emergency room who also have documented chronic or acute pain

1. Age greater or equal to 18
2. History of chronic or acute pain with or without opioid use disorder
3. Expected length of stay at least 2-3 days at the time of recruitment
4. Able to read and understand the informed consent form

- **Exclusion Criteria**

1. Since this is a feasibility pilot, only English-speaking participants will be eligible.
2. Cognitive impairment (Intellectual Disability Disorder or Dementia)
3. Patients who have a legal guardian
4. Participants with a history of skin disease (e.g., psoriasis) involving the ear, adhesive allergy, recent scar tissue on ear, or current abrasions or cuts on ear,
5. Use of some types of hearing aids (obstructing the placement of beads)

- **Sample Size**

A total of between 10-20 patients will be recruited from Atrium Health BH Charlotte ED Observation unit

### **Interventions and Interactions**

Terms: AA = Auricular acupressure

Acupressure pad= hypoallergenic adhesive pad containing a 2 mm Vaccaria seeds (Earseeds®)

Acupoint = specific area of body where acupressure is applied.

BAApress= Battlefield Auricular Acupressure

- Participants will be informed of the study once they are identified by the behavioral health care team, which includes patient's psychiatric provider and medical consultation provider as an appropriate candidate.
- Informed consent will be obtained by study personnel or the interventionist, the BAApress interventionist will confirm consent for participation.
- A study team member will perform visual analogue Scale and Brief Pain Inventory with the participant to establish baseline pain score and impact pain has on general activity, mood, walking ability, normal work, relationship with other people, sleep and enjoyment.
- The participant will be asked to also complete baseline questionnaires prior to the initiating placement of the AA including data collection form and General Anxiety Disorder Scale (GAD-7)- A self-administered 7 item scale that draws from DSM-V criteria for general anxiety disorder (GAD) to identify GAD and measure symptom severity. It is routinely used to measure changes and track treatment progress.
- BAApress interventionists will record the time from the moment they meet with the patient in an available room for the purposes of placing acupressure pads and activating each pad until they exit the room. BAApress interventionists will make notation if recorded time includes activity unrelated to placement of acupressure pads. After placement of acupressure pads, BAApress interventionist will enter procedure note in a shared specific file for interventionist and complete the REDCap nurse questionnaire.

**Day 1**

The baseline and day 1 activity can take place on the same day, but it is not required. Following completion of informed consent and baseline questionnaires, the trained BAApress interventionist nurse will place the acupressure pads.

- If the ear contains lesions, skin breakdown, or show signs of irritation, the acupressure pads will not be placed, and this will be noted in the study record.
- If the participant consented to the recording portion of the study, they will be reminded of the process and the BAApress acupressure nurse will confirm that the participant still agrees to participate in the recording portion of the study.
- Acupressure pads will be placed prior to any pain medication.
- A total of 10 adhesive acupressure pads will be placed, 5 acupressure pads per ear. Patients will be given a handout showing location of each point where acupressure pad will be placed. The pads will be placed bilaterally on the following 5 auricular sites: 1) Cyngulate gyrus, 2) Thalamus, 3) Omega 2 4) Point Zero, and 5) Shen Men. These sites were selected based on the Veterans Administration Battlefield Auricular Acupressure Protocol for acute and chronic pain. This is the protocol the Veterans Administration uses for acupressure therapy for acute and chronic pain management and is taught to both nurses and physicians.
- Each ear will be cleansed with alcohol, beginning at the base of the ear (lobule) to the apex. The acupoints will be visually located and marked with a sterile surgical marker.
- The pads will be placed by visual identification of the preselected acupoints as per BAApress protocol. The pads will be placed on the identified site by hand or with the assistance of tweezers, with the seed portion of the pad aligning with the identified acupoint.
- To secure the pad, gentle but firm pressure will be applied to the pad, making sure that pressure is applied to the entire pad.
- After placement, the interventionist will apply moderate pressure to each acupressure pad for 30 seconds (total time 2.5 minutes per ear). Both right and left ear site will be stimulated at the same time with pressure in the following order: 1) Cyngulate gyrus, 2) Thalamus, 3) Omega 2, 4) Point Zero, and 5) Shen Men.
- Participants will tell the BAApress interventionist nurse when they feel a tingling sensation in the ear or feel moderate tenderness or pressure as confirmation

that moderate pressure is being applied. Description of sensations felt by participant will be recorded by the BAApress interventionist.

- The BAApress interventionist will document pad placement and activation in EPIC.
- BAApress interventionist will review with participant how and when to activate each pad and give participant a picture of a right and left ear with the acupressure points location on each ear. Participants will be reminded to gently press on each pad for 30 seconds at least three times a day to activate for a total of 3 days.
- If the acupressure pads fall off before day 3, they will not be replaced. The BAApress interventionist will record the missing pad/pads.
- After completion of day 3 study activities, the study team will remove the acupressure pads by gently pulling on the edges of the pad and lifting off with their fingers or using tweezers to loosen the pad if needed.
- If participants are discharged prior to 3 days, they will be contacted via telephone call by study personnel and/or via text messaging depending on participant preference to remind them to complete the questionnaire and to activate their pads 3 times per day.
- At the end of the third day, the study personnel will call the patient, or they will receive a text letting them know the study team needs to arrange a telephone call to provide instruction on how to remove the acupressure pads. If participant cannot be reached by phone, they will be instructed on removing pads by gently pulling on the edges of the pad and lifting off with their fingers or using tweezers to loosen the pad if needed. Participants will be reminded to complete final post intervention questionnaires after removal of pads that study personnel will review with them.
- The BAApress interventionist nurse may record and take pictures of the treatment visit. These recordings will be used to ascertain fidelity to the intervention protocol as it relates to a) proper placement of acupressure seeds and b) provision of instructions to the participant.
- Each study participant will be asked to sign a separate consent giving permission for the intervention to be recorded and used for education and research purposes. The recordings will be done to limit exposure of the study participant's face.

- The study team will perform Visual Analogue Scale (VAS) and Brief Pain Inventory with participants one to two times a day for 3 days.
- The study team will have the participant complete GAD-7 every morning for 3 days.
- The study team will complete BAApress Questionnaire daily with participant every morning for 3 days.

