### **Secondary Outcomes to be measured:**

- Pain medication usage. Trajectory of am and pm pain scores
- General Anxiety Disorder Scale (GAD-7). Patients are asked to rate the frequency of anxiety symptoms daily on a Likert scale (0-3). In general, patients with GAD or other common anxiety disorders exhibit GAD-7 scores of 10 or greater.
- Pain Management Satisfaction to determine patient satisfaction
- Acupressure Acceptability questions - We will ask acceptability questions. "How satisfied were you with how your pain has been treated?" using the Likert scale to measure "Very satisfied =5, Satisfied=4, Somewhat satisfied = 3, Somewhat dissatisfied= 2, Dissatisfied 1, Very Dissatisfied 0." Would you consider using auricular acupressure in the future for pain or if recommended by your nurse or physician? a. No, would not use again (Score of 0) b. Maybe (Score of 1), c. Yes, I would consider using in the future (Score of 2) 3. Is there anything else you would like to tell us that may be helpful for us to know regarding ear acupressure? (Each answer will be collected and assessed for future studies).
- BAA Press placement survey (interventionists only): The Interventionist (Acupressure nurse) will be asked to capture time related to completion of study tasks and other qualitative questions to assess overall feasibility.
- Additional Data collection: contact information, relevant demographic data that will be recorded are: DOB, age, gender, ethnicity/race. Relevant medical history will be duration of pain medications including narcotic use (in years) and comorbid chronic or acute pain diagnoses.

Study activity	Baseline a	Day 1	Day 2	Day 3/End of study
Informed Consent signed	x			
Data Collection Form	x	x	x	x
Complete Baapress Questionnaire	x	x	x	x
Administer or record Pain score assessment (VAS) b	x	x	x	x
Brief Pain Inventory	x	x	x	x
Pain Management Satisfaction				x
Generalized Anxiety Disorder Scale (GAD-7)	x	x	x	x
Acupressure placement and patient education		x		
*Optional interventionist recording of AA placement d		x		
Study team collect completed questionnaire				x
Compensation administration				x
BAA press placement survey (interventionist only)	x	x	x	x

a Baseline and Day 1 can be completed on the same day. Baseline activities are to be completed prior to Acupressure administration.

b The study team will perform the pain score assessment with the participant two times a day for three days.

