### **Subject Recruitment Methods**

To assist with recruitment. Patients when admitted to Atrium Behavioral Health Emergency Room may be identified by screening behavioral health treatment team and referred to study personnel.

Study personnel will review eligibility and approach patient regarding participation. Only eligible patients willing to complete all survey's pre and post procedures and provide written consent will participate. The study team will ensure that the participant understands the voluntary nature of participating in the research study and that study participation study will not affect the care that they will receive.

The study personnel will maintain a record of eligible study participants. This list will include name, MRN, psychiatric and pain diagnosis, and will be kept in a secure file on a secure computer and only accessible to study staff. The file of eligible participants will be destroyed at the end of recruitment.

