### **Reporting of Unanticipated Problems, Adverse Events or Deviations**

Any unanticipated problems, serious and unexpected adverse events, deviations or protocol changes will be promptly reported by the principal investigator or designated member of the research team to the IRB and sponsor or appropriate government agency if appropriate.

Appendix A: Data Collection Form 3 9 23

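### Read literally, the Day 1 rule to place pads before any analgesic can delay a due or requested dose, and the visible text does not tie dose times to the pain scores

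*Combined protocol and SAP*

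**What the plan says.** Under Interventions and Interactions, Day 1, one step reads "Acupressure pads will be placed prior to any pain medication". Neither that step nor any other visible section makes an exception for a scheduled dose, a patient request or severe pain. On the timing of visits, the same section says "The baseline and day 1 activity can take place on the same day, but it is not required". The schedule's first footnote requires baseline activities to be finished before the pads go on. Placement therefore follows consent, the VAS, the Brief Pain Inventory (BPI), the GAD-7 and the data collection form.

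The inclusion criteria admit patients with "History of chronic or acute pain with or without opioid use disorder" and require no analgesic-free period. The Background describes the intervention as tested "as an adjunct to medication for pain management for psychiatric Emergency Department Observation patients". Subject Recruitment Methods says participants will understand that "study participation study will not affect the care that they will receive". The reporting section says that "deviations or protocol changes will be promptly reported", without defining a deviation.

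Objective 2 asks whether the intervention will "lower pain scores and decrease pain medication usage". The matching entry under Secondary Outcomes is "Pain medication usage. Trajectory of am and pm pain scores", with no unit, observation window or comparison period. The only medication item with a unit is duration of past use, in years. There is no control group. The Analytical Plan is descriptive, and its estimates are meant to inform the power of later studies.

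**The concern.** There are two linked problems. The first is participant protection. A nurse with a dose due and the pads not yet placed must either hold the dose or give it and wonder whether that is a reportable deviation. The participants were selected for pain, so the situation is likely to arise.

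The second is interpretation. A dose given shortly after placement can lower the next VAS or BPI score, and those are the primary outcomes. If dose times are not recorded alongside scores, that relief may be credited to the pads. A decrease in medication also needs something to decrease from, and no pre-placement period is visible. Any blurred estimate would carry into the planning of later studies.

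**Working it through.** There is no stated figure to reproduce. The check is a reading of every visible mention of pain medication, followed by an illustration on labelled assumptions.

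**1. Is there an exception anywhere?** No. The adjunct purpose and the care assurance point away from withholding, but neither tells bedside staff that a due dose may come first.

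**2. What does the rule mean?** It could refer to the next dose, the first dose that day, or any dose since admission. The last cannot be met by someone already medicated on the unit, and such patients are not excluded. The next dose is the workable reading, but the text does not say so.

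**3. How long could a dose wait?** The only timed step is pressing: 5 points × 30 s = 150 s = 2.5 minutes, both ears together. Consent, questionnaires, ear cleaning, marking, placement and waiting for the nurse have no stated duration. The delay cannot be calculated.

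**4. Where does the dose fall?** On a same-day visit the order is baseline score, placement, dose. If the dose precedes the first post-placement score, it lies between the two scores being compared. If baseline and placement are on different days, doses between them also lie in that interval. Changing the rule alone would not alter this: a dose given after baseline scoring but before placement falls in the same gap.

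**5. Illustration for pain scores.** Assume a 0–10 scale and a dose that lowers one score by 1–2 points. The cohort mean at that assessment then moves by (drop ÷ number of participants) per affected participant: 1/20 = 0.05 to 2/10 = 0.20 points, for the planned 10–20 participants. If everyone were affected, it would move by the full 1–2 points. The schedule footnote sets the VAS twice daily for three days, 2 × 3 = 6 scores. The procedures text allows once or twice daily for VAS and BPI, or 3 to 6.

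**6. Illustration for usage.** Assume regular 4- or 6-hourly dosing and one held dose. Over 72 h the expected count is 72/4 = 18 or 72/6 = 12.
- Counted from placement, a held dose with later doses on their original clock gives 19 or 13. If later doses shift, or the held dose is omitted, the count stays at 18 or 12.
- Counted from the time due, only omission changes the count, to 17 or 11.

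The change is at most one dose, 1/18 = 5.6% to 1/12 = 8.3% of that participant's total, with no fixed direction.

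**7. Is there a usable comparison period?** The Informed Consent section places consent at admission to the Observation unit. If placement follows promptly, the in-unit record beforehand is short. At 6-hourly dosing, 24 h holds 24/6 = 4 doses, 12 h holds 2 and 6 h holds 1. One or two doses are a poor basis for claiming a decrease.

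**The case against.** The strongest reply is that the line only orders the steps. It does not tell anyone to withhold, delay or skip a dose. The patient's own psychiatric and medical providers are part of the team that identifies candidates, and nothing gives study staff control over analgesia. Since baseline and placement may fall on different days, a due dose can be given on time and the pads placed before the next one. All of this stands. A reader might infer that the plan means to withhold pain relief, but the documents do not support that. What remains is an unqualified instruction whose safe reading has to be guessed.

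The second reply concerns data capture. The Data Collection Form and the BAApress Questionnaire are both scheduled at baseline and on Days 1 to 3, and their contents (Appendices A and B) are not shown. They may already record drugs, doses and times, so it would be wrong to infer that the study does not collect them. Form fields alone would still not say how usage is summarised or what it is compared with.

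Third, the lack of a control group is openly declared and limits attribution whatever the dosing order. That is also right: the Day 1 line is not the sole source of the confounding. Recording and flagging make it visible but do not remove it.

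**Conclusion.** The point holds, at minor to moderate severity. The Day 1 rule can, on its literal wording, delay analgesia that is due or requested, against the plan's own purpose and assurance. Medication usage has no visible definition or pre-placement reference, and no visible text links dose times to pain scores.

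The size is unknown from the documents. The figures of 0.05–0.20 points per affected participant and at most one dose in 12 to 18 rest wholly on assumed dosing intervals, drug effect and score scale. They show scale only and should not be read as a bias of known size or direction. The case for change rests on participant protection and on keeping Objective 2 interpretable. The data-capture part is conditional on what the unseen forms contain.

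**What to change.** Replace the Day 1 line with: *Analgesia that is due or requested is never delayed for pad placement; pads are placed before the next dose where feasible, and a dose given before placement is not a deviation.*

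If Appendices A and B do not already do so:
- Record drug, dose and time of the last analgesic before placement and of each dose through Day 3.
- Record the clock time of each VAS and BPI.
- Flag participants who had a dose between the baseline score and the first post-placement score. If the two visits are on different days this may be most of those on regular analgesics, so show the recorded times as well as the flag.
- After early discharge, ask about home doses at the telephone or text contacts already planned, and mark them as self-reported.

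Report usage after placement descriptively against whatever documented pre-placement period exists, stating its hours for each participant. Where that period is too short, report usage without claiming a decrease.

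The cost is one protocol sentence, an IRB amendment and perhaps a few form fields. In-unit dose times can come from the medical record. The downsides are more variable time from last dose to placement, and short or self-reported medication windows for some participants.
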